### 3.2 Study design

[figure not shown]
This is a

- Three arm (placebo, lanifibranor (IVA337) 800 and 1200 mg/day),
- Randomised (1:1:1, stratified on diabetes),
- Placebo-controlled,
- Double-blind,
- Parallel-assignment,
- Dose-range,
- Multicenter: at least 60 sites across 13 European countries (i.e., Belgium, France, Italy, Spain, United-Kingdom, Poland, Czech Republic, Germany, The Netherlands, Switzerland, Austria, Portugal, Slovenia), Canada, Australia, Mauritius and the United States of America (USA) will participate,
- 24-week treatment study.

The study will require at least 30 months of enrolment period, to randomise 225 patients (i.e. at least 300 screened patients), for a total study duration of up to 38 months.

The overall study design is shown in Figure below.

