#### *4.1.5 Treatment groups comparison*

For statistical tests, the type I error risk of these will be set at 5% (2-sided) without adjustments for multiplicity testing, unless specified otherwise.

P-values will be presented with 3 decimals. Any p-value less than 0.001 will be presented as <0.001, even if it would normally round up to 0.001.

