Dose-response relationship for **qualitative variables** will be estimated using the Cochran-Armitage trend test via the LOGISTIC procedure (See Reference 5). Within this model, dose will be considered as a quantitative covariate (0 mg, 800 mg and 1200mg) and diabetic status as a qualitative covariate (Presence, Absence). The p-value assessing the significant dose-response relationship at week 24 will be provided based on this model (Score test).

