## 4.2 Sample size calculation

The expected rate of responders according to the retained definition was estimated to 10% for the placebo by a group of clinical experts. An excess rate of responders of 20% was accepted as clinically pertinent. It corresponds to a multiplication of chance of success (responders) of 3 and a NNT (Number Needed to Treat) of 5. The sample size required to reach a power of at least 80% is 72 patients per group with a two-sided alpha of 0.025 (adjustment for multiplicity). The sample size is sensitive to the rate of responders in the placebo group. For example, if the rate of responders is 15% instead of 10% then 85 patients are required. If the true rate is lower than 10% then less patients may be sufficient. The sample size is therefore rounded in the conservative side of 75 patients per group.

Based on the experience of previous clinical trials, it is estimated that 100 patients per group will need to be screened to randomise 75 patients after central reading of liver biopsy confirms the NASH diagnosis and activity (screening failure rate of 25%). However, as detailed in section 3.5, the observed screening failure rate was of 72%), consistent with all other clinical trial performed in NASH with such a high screening failure rate.

In case the end of study liver biopsy slides are not available or not interpretable in more than 5% of patients, an amendment will be submitted to increase sample size accordingly.

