### 5.2.2.4 Secondary analyses of the primary endpoint

#### **Dose-response relationship**

Moreover, the dose-response relationship will be assessed on the FAS (Primary imputation method and Observed cases under treatment), and on the PP (Observed cases under treatment) according to method detailed in section 4.1.5 (Cochran-Armitage test using PROC LOGISTIC with adjustment on diabetic status).

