### **Evaluation of treatment effect after adjustment on the relative change in weight from baseline**

In order to evaluate the treatment effect after adjustment on the relative change in weight from baseline, a LOGISTIC model will be run on the FAS - Observed Cases under treatment. For this model, treatment will be considered as a quantitative covariate (placebo, 800 mg and 1200mg), diabetic status as a qualitative covariate (Presence, Absence) and weight variation as a quantitative effect. The p-value assessing the significant dose-response relationship at week 24 will be provided based on this model, as well as the OR for a change of 2% in weight.

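### SAP 4.1.5 takes the dose-response p-value from an unspecified score test of a model holding dose and diabetes; read literally, it is a 2-df joint test

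*SAP*

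**What the plan says.** The rule is at the end of SAP 4.1.5, in the paragraph on dose-response for qualitative variables.

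- The test is named as a "Cochran-Armitage trend test via the LOGISTIC procedure", with the SAS paper in Reference 5 cited for the method.
- The model holds two terms: "dose will be considered as a quantitative covariate (0 mg, 800 mg and 1200mg) and diabetic status as a qualitative covariate (Presence, Absence".
- The result is read off as follows: "The p-value assessing the significant dose-response relationship at week 24 will be provided based on this model (Score test".

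Section 5.2.2.4 applies this to the primary endpoint and describes it as "Cochran-Armitage test using PROC LOGISTIC with adjustment on diabetic status". Sections 5.2.3.1 to 5.2.3.4 and 5.2.3.14 apply it to NASH improvement, NASH resolution without worsening of fibrosis, fibrosis improvement, resolution with fibrosis improvement, and the two-stage Ishak improvement. Each of the six endpoints is analysed three ways: FAS with primary imputation, FAS observed cases under treatment, and PP observed cases under treatment. That makes 6 × 3 = 18 dose-response p-values.

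No separate error rate is set for these tests, so the general rule in 4.1.5 applies: "the type I error risk of these will be set at 5% (2-sided) without adjustments for multiplicity testing, unless specified otherwise". Neither document gives a null hypothesis, degrees of freedom, a STRATA statement or code for them.

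**The concern.** A logistic score test reproduces the Cochran-Armitage test only when dose is the sole covariate. Once diabetic status is also a covariate, the score statistic of the model tests whether both coefficients are zero. SAP 4.1.5 attaches the score test to the model, not to the dose term. A programmer who fits that model and copies its overall score line would report a joint test under a dose-response label.

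Two things could follow. If diabetes predicts response, the p-value can be small although the arms do not differ. If diabetes does not predict response, the extra degree of freedom costs power. The trial is a dose-range study, and these p-values are its formal trend evidence on histology.

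**Working it through.** **Inputs from the documents.** Model terms, dose scores 0/800/1200 and the 5% two-sided level: SAP 4.1.5. Allocation, "Randomised (1:1:1, stratified on diabetes": SAP 3.2. Patients randomised, 247: SAP 3.5. Planning rates of 10% and 30%: SAP 4.2.

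**Inputs assumed.** The documents give no share of diabetics (protocol 9.3 sets no quota) and no response rate by diabetic status. The calculations assume 40% diabetic, 20% responders overall, and diabetes odds ratios from 1 to 3.

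**The plan's own figure.** The documents give no figure for the dose-response test. The sample size does reproduce: "The sample size required to reach a power of at least 80% is 72 patients per group with a two-sided alpha of 0.025". With unpooled variance, n = (2.2414 + 0.8416)² × (0.10×0.90 + 0.30×0.70) / 0.20² = 9.505 × 7.5 = 71.3, so 72. For 15% against 35%, 9.505 × 8.875 = 84.4, so 85, as SAP 4.2 states.

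**What the model-level score statistic is.** Let x be dose and d diabetic status, both centred, let r be response minus its overall mean p̄, and let v = p̄(1 − p̄).

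- Dose alone: (Σxr)² / (vΣx²), on 1 df. This is the Cochran-Armitage statistic.
- Dose and diabetes: U′(vX′X)⁻¹U, with U = (Σxr, Σdr), on 2 df.

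Randomisation is stratified on diabetes, so Σxd is close to zero. The 2-df statistic is then close to the trend chi-square plus a diabetes chi-square.

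**Worked data set with no dose effect.** Give every arm 5/45 non-diabetic and 9/30 diabetic responders. Over three arms N = 225, with 42 responders, p̄ = 0.18667 and v = 0.15182.

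- Dose part: 0, because the arms are identical.
- Diabetes part: (27 − 90×0.18667)² / (0.15182 × 90×135/225) = 10.2² / 8.198 = 12.69.
- Joint score test: 12.69 on 2 df, p = 0.0018.
- Dose coefficient adjusted for diabetes: 0, p = 1.00.

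**False-positive rate with 247 patients (82/82/83) and no dose effect.** The noncentrality of the joint test is approximately λ = N × 0.4 × 0.6 × (p_D − p_N)² / [p̄(1 − p̄)], where p_D and p_N are the diabetic and non-diabetic response rates. For an odds ratio of 2 with 20% overall, p_N = 15.5% and p_D = 26.8%. Then λ = 247 × 0.24 × 0.1132² / 0.16 = 4.75, and the chance of exceeding the 2-df critical value of 5.99 is 48%. Simulation agrees:

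| Diabetes odds ratio (assumed) | Joint 2-df score test rejects | Diabetes-stratified 1-df trend test rejects |
|---|---|---|
| 1 | about 5% | about 5% |
| 1.5 | about 20% | about 5% |
| 2 | about 49% | about 5% |
| 2.5 | about 73% | about 5% |
| 3 | about 87% | about 5% |

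Repeat runs differ from these figures by one to two percentage points.

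**Other assumed rates.** With 75 per arm, 40% diabetic and no dose effect (16,000 trials per row):

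| Non-diabetic / diabetic response | Joint 2-df | 1-df dose test, diabetes in the null model |
|---|---|---|
| 10% / 10% | 5.0% | 5.2% |
| 10% / 15% | 16.7% | 5.0% |
| 10% / 20% | 45.5% | 4.7% |
| 10% / 25% | 77.4% | 5.5% |
| 10% / 30% | 94.0% | 5.1% |

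Results with 50% diabetic are similar.

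**Power when diabetes has no effect.** With 247 patients and response rising linearly with dose from 10% on placebo to 30% at 1200 mg, power is about 91% for the 1-df test and about 85% for the joint test.

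**The case against.** The strongest reply is that the SAP never says global, joint or 2 df. A score test of dose with diabetic status kept in the null model has 1 df, is valid, and fits the same words. The stated purpose is to assess dose-response, and the description in 5.2.2.4 and the secondary-endpoint sections, "Cochran-Armitage test using PROC LOGISTIC with adjustment on diabetic status", points to dose given diabetes. Reference 5 and the appended table shells are not available here and might settle the matter. What PROC LOGISTIC prints by default is software knowledge and is not in the documents.

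This stands as far as intent goes: a dose-only test was very probably meant. It does not rescue the text. The p-value is assigned to the score test of a two-covariate model. The valid version needs either a STRATA statement or a named null model, and the SAP gives neither. A pre-specified test should not admit two different p-values.

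The reply is also right that inflation needs diabetes to predict response, for which the documents offer no figure. At an odds ratio of 1 the joint test holds its level.

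A reader might extend the point to the weight-adjusted logistic analysis in 5.2.2.4, which says "The p-value assessing the significant dose-response relationship at week 24 will be provided based on this model". That sentence names no score test, and the model has a third covariate, so neither the mechanism nor the figures above carry over.

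**Conclusion.** The concern holds as a defect of specification with a harmful literal reading. Taken as the model-level statistic, the SAP's score test is a 2-df joint test of dose and diabetes. It is not a trend test adjusted for diabetes. The false-positive rate for dose-response would then run from about 5% at an assumed diabetes odds ratio of 1 to about 87% at 3, with 40% diabetic and 20% responders also assumed.

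Three stronger conclusions are not supported:

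- **That the SAP prescribes the joint test.** It leaves the hypothesis open.
- **That the test must reject whenever diabetes is prognostic.** The figures are probabilities under assumed inputs.
- **That the trial's main conclusion is at risk.** SAP 5.2.2.1 rests the primary objective on the two CMH tests with the Hochberg procedure. The trend test was added in the SAP (4.6.4) as a secondary analysis and gates nothing. The sample size is unaffected.

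**What to change.** In SAP 4.1.5, before unblinding, state that the dose-response p-value is the 1-df trend test for dose within diabetes strata, and name one implementation:

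- the PROC FREQ CMH correlation statistic with scores 0/800/1200, stratified on diabetic status; or
- PROC LOGISTIC with STRATA on diabetic status and dose as the only covariate, reading the 1-df score p-value.

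Add that the global-null score statistic of the two-covariate model is not used. Sections 5.2.2.4, 5.2.3.1 to 5.2.3.4 and 5.2.3.14 already refer back to 4.1.5; align their short descriptions with the new wording. The cost is one sentence and one program line. It should be done before unblinding because choosing between the two p-values with results in hand would be data-dependent.

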#### 4.1.6 *Missing data*

##### 4.1.6.1 *General considerations*

Unless otherwise specified, missing data will not be replaced. In this case, the descriptive analyses of each variable will be based on the available data, i.e. Observed Cases (OC) analysis, considering missing data as non-informative. The number of missing data will be documented for each analysis.

##### 4.1.6.2 *Dates*

Imputation rules for missing first dose date / last dose date:

- Missing first dose date / last dose date at intermediate visits will remain missing
- Missing first dose date at time of randomisation will be imputed as the date of randomisation
- Missing end dose date at time of Visit 3 will be imputed as follow:
  - o If the patient prematurely withdrew from the study due to AE and if the month/year of EOT date is equal to month/year of start date of AE, then the EOT date will be replaced by the start date of AE
  - o If the patient prematurely withdrew from the study due to a reason other than AE, then:
    - If last contact date is missing then the date of last visit performed under treatment (V3 or V2 or V1) will be considered as the EOT date
    - If last contact date is provided, then it will be considered as the EOT date.
  - o If the patient completed the treatment period, and if the month/year of EOT date is equal to month/year of date of Visit 3, then the EOT date will be replaced by the date of Visit 3

Imputation rules for partial or missing start dates for AE:

- If month and year are present:
  - If month/year of AE corresponds to month/year of a physical examination with an abnormal value and if verbatim of AE corresponds to the finding of this physical examination, then impute the day by the day of physical examination with an abnormal value
  - Otherwise, if month/year of AE corresponds to month/year of first treatment intake then impute the day with the day of first intake of treatment
  - Otherwise, impute by the first day of the month
- If only the year is present, impute by January 1st of that year. If the year is the same as the year of the date of first dose, impute by the day of first intake of treatment.
- If the start date is entirely missing, impute by the day of first intake of treatment. If after imputation AE start date is posterior to AE end date, then imputed start date should be replaced by AE end date.

Imputation rules for partial or missing start dates for concomitant medications and medical history:

- If the month and year are present, impute the day by the first of that month. If the month and year are the same as those of the date of first dose, impute the day with the day of first intake of treatment.
- If only the year is present, impute by January 1st of that year. If the year is the same as the year of the date of first dose, impute by the day of first intake of treatment.
- If the start date is entirely missing, impute by the day of first intake of treatment. If after imputation concomitant medication or medical history start date is posterior to concomitant medication or medical history end date, then imputed start date should be replaced by concomitant medication or medical history end date.

Imputation rules for partial or missing stop dates for AE, concomitant medication and medical history:

- If the month and year are present, impute the day by the last day of that month.
- If only the year is present, impute by December 31st of that year.
- If the stop date is entirely missing, assume the event or medication is ongoing.

For any partial dates other than start and stop dates, for AE, concomitant medical and medical history:

- If only month and year are present, impute by 15th of that month,
- If only the year is present, impute by July 1st of that year
- If date is fully missing, impute by corresponding visit date.

#### 4.1.6.3 Main criteria

The following method of missing data imputation will be used for main efficacy criteria analysis (qualitative endpoints: Responder vs. Non-responder):

##### 1. Primary imputation method

Patients with a missing data will be considered as Non-responder.

##### 2. Secondary imputation method

Patients with a missing data will be considered as Non-responder in case of premature treatment withdrawals due to: Adverse event or Other: Lack of efficacy. The other reasons will be clearly reviewed during Blind Data Review Meeting (BDRM) to identify 'Lack of efficacy'. In all other cases, missing data will remain missing.

##### 3. Observed cases (OC)

Missing data will remain missing, only observed cases will be used.

##### 4. Observed cases under treatment (OCUT)

###### Biopsy:

Only observed cases within 14 days after study treatment last intake will be considered:

- Missing data will remain missing
- Any biopsy data collected more than 8 days after study treatment last intake will not be considered as assessed under treatment, meaning will be considered as missing for the OCUT analysis

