###### Note:

- Data collected at Visit 3 being an early treatment discontinuation, should not be taken into account for Week 24 (i.e. actual V3) data descriptions
- For OCUT analysis where data available at Week 28 (i.e. V4) should be described, all Week 28 (i.e. V4) data that are within 4 weeks  $\pm$  2 weeks compared with Week 24 (i.e. V3) are to be taken into account.  
Data collected at Visit 4 being the visit following an early treatment discontinuation, should not be taken into account for Week 28 (i.e. actual V4) data descriptions
- For all analysis based on biopsy data, data collected at actual V3 should be taken into account as well as data collected at Visit 3 being an early treatment discontinuation.

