#### 4.3.5 Evaluable patient population (EPP)

The evaluable patient population will consist of the FAS after exclusion of all patients without post-randomization efficacy assessment (SAF score at visit 3).

- All patients who prematurely discontinued the study treatment:
  - o due to a reason linked to study treatment intake (adverse event) or lack of efficacy (recorded in ‘Other’) will be included in the EPP. In this case, the patient will be non-responder (see ‘Secondary imputation method’ in section 4.1.6.3).
  - o for a reason not linked to study treatment intake (such as lost to follow-up or consent withdrawal) will be excluded from the EPP.

The reasons of study treatment premature discontinuation will be solely reviewed during BDRM to correctly define the EPP.

[figure not shown]
- Patients that completed their study treatment up to Visit 3:
  - o with an efficacy assessment at Visit 3 (biopsy performed, readable and performed within 14 days following last intake) will be included in the EPP.
  - o without efficacy assessment at Visit 3 (biopsy not performed because patient refusal, biopsy not readable, biopsy not performed within 14 days following last intake...) will be excluded from the EPP.

The same rule will be applied for other binary efficacy variables.

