#### - **Patient still under treatment, if visit performed**

A patient will be considered as “still under treatment” at a given visit if last treatment intake is  $\geq$  visit date - 3.

- **Patient still ongoing, if visit NOT performed**

A patient will be considered as “still ongoing” at a given theoretical visit if another visit has been performed after this missing one.

- **Patient still under treatment, if visit NOT performed**

A patient will be considered as “still under treatment” at a given theoretical visit if last treatment intake is  $\geq$  theoretical visit date - 3.

- **Study duration (months)**

Study duration (in months) is defined as the time between the randomisation date and the date of End of Study:  $(\text{Date of End of Study} - \text{randomisation date} + 1) / 30.4375$ .

- **Study duration (weeks)**

Study duration (in weeks) is defined as the time between the randomisation date and the date of End of Study:  $(\text{Date of End of Study} - \text{randomisation date} + 1) * 52 / 365.25$ .

- **Premature treatment withdrawal**

A patient will be considered as having prematurely discontinued study treatment if the reason for end of treatment is different from “Treatment period terminated as per protocol”.

- **Completer patients**

A patient will be considered as a completer if he/she did not prematurely withdrawn treatment.

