#### 5.1.1 Patients disposition

The number (%) of patients included in each population will be described overall and then by country: screened patients, non-randomised patients, randomised patients, FAS, EPP, safety patients and PP patients. Percentages will be calculated over the number of randomised patients.

First Patient First Visit, Last Patient First Visit and Last Patient Last Visit will also be described overall and then by country. "First Visit" will be defined as the screening visit (V-1).

The reasons for non-randomisation will also be described among the non-randomised patients, consisting of screening failed patients.

In addition, in order to have an overview of patients' disposition, the following elements will be described by treatment group and overall in the FAS for each post-randomisation visit:

- Number (%) of patients who performed the visit (Yes/No)
  - o If Yes, Number (%) of patients still under treatment (Yes/No)
  - o If No:
    - Number (%) of patients still ongoing (Yes/No)
    - Number (%) of patients still under treatment (Yes/No)

Due to the CRF design, Visit 3 was either completed per protocol and performed at week 24, or performed as part of early termination visit. For analysis, visit 3 will be splitted in 2:

- Visit 3 performed as part of early termination visit (i.e. premature EOT)
- Visit 3 performed as part of week 24 visit.

Same strategy will be applied for visit 4:

- Visit 4 performed after a visit 3 performed as part of early termination visit (i.e. follow-up visit following premature EOT)
- Visit 4 performed at week 28 after a visit 3 performed as part of week 24 (i.e. follow-up visit following treatment completed until week 24).

Additionally, for visit 4 performed after a visit 3 as part of week 24, it will be detailed whether visit 4 has been performed within 4 weeks +/- 2 weeks after visit 3 or not.

In order to have an overview of biopsies' disposition, the following elements will be described at Visit 3 by treatment group and overall in the FAS

- Number (%) of biopsies available (Yes/No)

- If Yes, Number (%) of biopsies still under treatment (Yes/No), i.e. within maximum 14 days after last intake
- If No, Number (%) of biopsies non-available (non-readable, patient refusal, premature permanent treatment discontinuation)

Additionally, patients' treatment status (Treatment completed, Treatment prematurely withdrawn) at time of study end will be described in the FAS overall and by treatment group.

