### 5.2.2.2 Sensitivity analyses

Several sensitivity analyses will be performed on the primary criterion as detailed in table below. Each time, descriptive analysis and evaluation of treatment effect (each dose versus placebo) will be performed as detailed in section 5.2.2.1.

To be confirmed. Indeed qualitative endpoint and not quantitative one => CMH and not MMRM ....

Analysis population	Treatment group	Missing data replacement
FAS	Actual treatment received	Observed cases under treatment*
Randomized set	Randomized treatment assigned	Primary imputation method
PP	Actual treatment received	Observed cases under treatment
EPP	Actual treatment received	Secondary imputation method
FAS	Actual treatment received	Observed cases

\* This analysis corresponds to analyses on completers (biopsy at week 24 performed, within maximum 14 days after last intake).

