### 5.2.2.3 Analysis by subgroups

Descriptive analysis (number, % with its 95% confidence interval) will be performed in the FAS (primary imputation method) and among completers (Observed cases under treatment) as detailed in section 5.2.2.1 for the following subgroups of interest:

- Biopsy length at baseline ( $\leq 8$ ,  $>8$  mm)
- SAF-A score at baseline (A2-A3, A4)
- CRN-F score at baseline (F0-F1, F2-F3)
- NAS score at baseline ( $<6$ ,  $\geq 6$ )
- BMI at baseline (Obese, Non-obese)
- Metabolic syndrome at baseline (Yes, No)
- Insulin-resistance status at baseline (Yes, No)
- Sex (Male, Female)

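### SAP 4.1.6.3 states the on-treatment biopsy window for OCUT as both 14 days and 8 days, and the set is mislabelled as completers; the primary FAS analysis is not affected

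*SAP*

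**What the plan says.** SAP 4.1.6.3, item 4 (OCUT), under Biopsy, opens with: "Only observed cases within 14 days after study treatment last intake will be considered". The second bullet beneath it reads: "Any biopsy data collected more than 8 days after study treatment last intake will not be considered as assessed under treatment", and it goes on to treat such data as missing for the OCUT analysis.

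Elsewhere the SAP uses one window:

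- 5.1.1, biopsy disposition table: "biopsies still under treatment (Yes/No), i.e. within maximum 14 days after last intake".
- 4.3.5, evaluable patient population (EPP): "biopsy performed, readable and performed within 14 days following last intake".
- 5.2.2.2, footnote to the FAS OCUT row: "This analysis corresponds to analyses on completers (biopsy at week 24 performed, within maximum 14 days after last intake". The same footnote recurs in 5.2.3.1 to 5.2.3.5, 5.2.3.6.1, 5.2.3.7.1 and 5.2.3.14, nine in all.

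The footnotes call the OCUT set *completers*. So do six subgroup sections (5.2.2.3, 5.2.3.1 to 5.2.3.4 and 5.2.3.7.1), with wording such as "among completers (Observed cases under treatment". SAP 4.5.2 defines that word: "A patient will be considered as a completer if he/she did not prematurely withdrawn treatment". The Note closing 4.1.6.3 says that, for all biopsy analyses, "data collected at actual V3 should be taken into account as well as data collected at Visit 3 being an early treatment discontinuation".

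**The concern.** Two sentences under one heading give different answers for the same patient. A biopsy ten days after the last tablet is to be considered under the first sentence and set to missing under the second. If the bullet is followed, that patient is counted as still under treatment in the disposition table and as not assessed under treatment in the efficacy tables.

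The consequence is an unfixed analysis set. Which patients enter OCUT depends on which sentence is followed, and a window left open after unblinding could be chosen with the results in view.

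The label adds a second, smaller problem. A patient who stopped early and had a biopsy inside the window belongs to OCUT under the Note but is not a completer under 4.5.2, so a table headed *completers* would misdescribe its denominator.

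**Working it through.** **1. The two rules applied day by day** (lag from last intake to biopsy):

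| Lag (days) | Lead sentence: kept if ≤ 14 | Bullet: missing if > 8 | Agree? |
|---|---|---|---|
| 7 | kept | kept | yes |
| 8 | kept | kept | yes |
| 9 | kept | missing | no |
| 14 | kept | missing | no |
| 15 | dropped | missing | yes |

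The conflict is exactly days 9 to 14.

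**2. Which number is the outlier.** The 8-day figure occurs once. The 14-day figure occurs in the lead sentence, the EPP definition, the disposition table and nine footnotes. The neighbouring rule for all other procedures has the same two-part layout and uses 3 days in both parts, so the layout is not a deliberate two-tier rule.

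**3. What depends on the cut-off** (SAP 5.2.1 and the sections it summarises):

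- FAS OCUT sensitivity analyses: 1 primary + 11 secondary rows = 12 rows. Two rows hold two variables each (improvement and no worsening, 5.2.3.7.1), giving 14 binary variables.
- PP OCUT analyses, and the subgroup tables run on OCUT.
- Dose-response on OCUT for six endpoints (5.2.2.4, 5.2.3.1 to 5.2.3.4, 5.2.3.14).
- 1200 v 800 mg comparisons on OCUT (primary endpoint in the 5.2.1 table; 5.2.3.1 to 5.2.3.5).
- The weight-adjusted logistic model (5.2.2.4), run on OCUT only.
- The main descriptive analysis of change in CRN-S, SAF-A, CRN-I, CRN-B, CRN-F and modified Ishak (5.2.3.6.2, 5.2.3.7.2).

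Not affected: the primary analysis. It uses the FAS and counts missing as non-response (4.1.6.3 item 1, 5.2.2.1). A Week 24 biopsy is available if SAF-A is non-missing at Visit 3 (4.5.4.1.3), with no day limit. The EPP has its own 14-day window.

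**4. Illustration of size.** No count for days 9 to 14 is given. Assume 0, 4 or 8 affected patients per arm, which is 0, about 5% or about 10% of 247/3 ≈ 82. This range has no source in the documents.

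The plan's sample size reproduces with the unpooled normal approximation at two-sided 0.025 and 80% power:

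- 10% v 30%: n = (2.2414 + 0.8416)² × (0.10×0.90 + 0.30×0.70) / 0.20² = 71.3, so 72 as stated.
- 15% v 35%: 84.4, so 85 as stated.

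Power from the same formula, Φ(0.20/√(0.30/n) − 2.2414): n = 82, 86%; n = 78, 84%; n = 74, 82%. If the affected biopsies respond like the rest, that small loss of power is the whole effect.

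Worst case for the contrast, taking 25/82 v 8/82 as the full data (20.7 points, p = 0.0009; unstratified chi-square without correction) and losing only active responders and only placebo non-responders:

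- 4 per arm: 21/78 v 8/78 = 16.7 points, p = 0.007.
- 8 per arm: 17/74 v 8/74 = 12.2 points, p = 0.048.

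The second case is remote. Under a random draw its probability is [C(25,8)/C(82,8)] × [C(74,8)/C(82,8)], about 1 in 78,000.

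**The case against.** **It can be programmed.** A reader might infer that OCUT cannot be derived from 4.1.6.3 at all. That goes too far. Applying both lines together is feasible: the stricter bullet governs and days 9 to 14 are missing. A reader of the whole SAP could equally spot 8 as a leftover. Double programming (4.1.3) is meant to expose such mismatches, at least for the most important datasets, and the dataset specifications it mentions are not among the documents. All of this stands, but it does not remove the conflict, because the literal reading contradicts the footnotes that define the same analyses.

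**It may affect few or no patients.** Protocol 4.1 makes the end-of-treatment biopsy part of Visit 3, with a ±3-day visit target (section 5). This also stands. The 82 per arm used above is the randomised number, so OCUT would start smaller.

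**The worst case does not overturn a result by itself.** A reader might infer that p = 0.048 fails because it exceeds 0.025. Under the rule in SAP 4.1.5, 0.025 applies to the smaller of the two p-values. If 0.048 is the larger, its critical value is 0.05 and it passes; it fails only if the other dose exceeds 0.05.

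**The label is defined where it is used.** The footnote explains its own term and does not cite 4.5.2. That softens the point, but the footnote's week 24 wording still conflicts with the Note that admits early-termination biopsies.

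**Conclusion.** The contradiction is real and should be corrected. SAP 4.1.6.3 gives two cut-offs for the same set, they disagree on days 9 to 14, and the 8-day figure conflicts with every other statement of the window. The label *completers* does not match the set that the Note defines.

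The size is unknown because no count of biopsies on days 9 to 14 is given; if there are none, no result changes. The figures above rest on an assumed range and only show how far OCUT results could move.

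Two stronger readings are not supported. The primary result is not at risk, since its analysis has no day window. Nor is the issue confined to sensitivity analyses: OCUT is the main analysis for six score-change endpoints, though these are descriptive.

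**What to change.** Before database lock:

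1. In SAP 4.1.6.3, OCUT, Biopsy, change 8 days to 14 days in the second bullet, or delete that bullet. Either brings it into line with the lead sentence, 4.3.5, 5.1.1 and the nine footnotes.
2. Replace *completers* with observed cases under treatment in the nine footnotes and six subgroup sections, and align the footnotes' week 24 wording with the Note on early-termination biopsies. If the sponsor in fact wants a set without early discontinuers, the Note has to change instead.

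The cost is one number and one label in 15 places, with no new data and no change to the primary analysis. An extra run of the primary endpoint in completers as defined in 4.5.2 is optional; protocol 9.7.4 names a completer set only among its examples.

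Two neighbouring matters are separate notes: the wording on early discontinuers in 4.3.5, and the mismatch between the 5.2.1 table (PP with primary imputation) and 5.2.3.7.1 (PP with OCUT) for the fibrosis improvement and no-worsening variables.
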